## 10.5 Definition of End of Study

The end of study is the date of the last study contact of the last recruited participant.

## **11.0 INTERVENTIONS**

#### 11.1 Description of tests:

#### Echocardiography

Echocardiography is a non-invasive bedside ultrasound test which, in this study, will take approximately 15minutes and has no radiation risk. This will be performed at 24hrs, 72hrs, 30 days (+/-5) and 90 days (+/-5). A standard operating procedure exists for performing echocardiogram. Additional information is provided in a PIS for participants. In accordance with local practice, PPE equipment is worn for this test. ECG electrodes and ultrasound gel can be a potential risk to the patient with regards to dermatological reaction/sensitivity, however both are hypoallergenic substances. If a patient is observed to have any reaction to these consumables alternatives will be sourced or patient will be excluded from study.

There are no drugs used in this study. There are no placebos or alternative treatments.

## Blood collection for NT-proBNPand High Sensitivity Troponin I

These tests will be performed locally by the blood sciences department (Pathology) at the Queen Alexandra Hospital Portsmouth. In-line with local protocols for these tests they will be collected and handled as follows:

- **1x gold topped SST blood tube** will be collected and will be sufficient for analysis of both analytes.
- This blood tube will be correctly labelled and sent to Pathology for analysis (as per routine samples)
- The SST blood tube will be allowed to clot for 30 minutes after collection.
- This will be centrifuged at **2000 x g for 10 mins at room temperature** to obtain serum before analysis and reporting.

## NT pro-BNP

The N-Terminal pro-B-type Natriuretic Peptide (NT pro-BNP) blood test will be performed on all participants on admission, day 30 and day 90. This is a validated and prognostic test for heart failure and it is of value in other forms of myocardial dysfunction. Results will be recorded in the CRF.

## High-sensitivity troponin

The high-sensitivity troponin test will be performed on all participants on admission, day 30 and day 90. This is a validated and prognostic test for ischemic myocardial injury and it is of value in other forms of myocardial dysfunction. Results will be recorded in the CRF. Both test are additional tests to standard care.

#### Haematology and biochemistry

Routine, standard care tests such as; haematology (haemoglobin, platelets, white cell count) and biochemistry (sodium, potassium, urea, creatinine, eGFR, bilirubin, albumin) will be taken at all stages/visits. The results will be recorded in the CRF.

## **12.0 ASSESSMENT OF SAFETY**

As this is a non-invasive study, no formal adverse event recordings or reporting will take place. The study is non-invasive and is low risk and low burden. However, if there are any incidents, for example allergy to ECG electrodes or ultrasonic gel, this will be recorded on the case report form (CRF). Attempts will be made at all time points to minimise pain, discomfort, distress, intrusion, inconvenience – asking for nursing assistance when required.

## 13.0 DATA HANDLING AND RECORD KEEPING

## 13.1Data Collection Forms.

The principal investigator (PI) will be responsible for ensuring the quality and security of all data recorded.

Data collection will be undertaken by the PI, investigators, specialist research nurses within the ICU and cardiology department and any other sub-investigators as per the delegation log. Data will come from a number of sources, and will require a variety of different collection and storage techniques:

Data source	Data collection
Echocardiographic imaging	Imaging data is collected and stored initially on the individual echo machine, and is then transferred onto a secure server (McKesson). The participants images are identified by a unique identifier number linked to the participant ID.
Medical notes, clinic letters and clinical databases	Entered onto paper data case report form (CRF) as source data
Consent form	Completed by participant and kept in medical notes
Laboratory reports – blood	Printout from electronic results system (ICE) to be kept as source data in medical notes, and results entered onto paper CRF

All CRFs will be kept in the Trial Master File (TMF), locked within the cardiology outpatient department. All data on the CRF and kept within the TMF will be anonymised. Source data which retains personal identifiable data will be stored within the participant medical notes which are also stored and archived according to standard procedures.

All electronic data will be stored anonymously on a secure network folder, accessible via a password-protected Trust computer

## 13.2 Data Management

Data management will be conducted by the investigators using clinical, access databases (Redcap) and excel documents, and will be accessed by named investigators only on Trust PCs that are password protected. Data will be monitored at the investigator site. If errors in clinical data are discovered during quarterly data entry checks, a query will be created. Queries are created when information is missing or is illegible and needs further clarification.

Query forms will be sent to the primary investigator for completion who will be acting as database manger for this study

The study database will be stored on a secure NHS server at Portsmouth Hospitals NHS Trust. All echocardiograms performed will be stored on 'McKesson' which is a server based cardiac image and information management system. This is the system in place for storing all echocardiograms performed at Queen Alexandra Hospital. Images from participants on this this study will be transferred to a separate private file which can only be accessed by principle investigator and is password protected .All images are stored under study number.

Trust standard operating policy is to archive study data for 15 years and then destroy.

## **14.0 DATA ANALYSIS**

## 14.1 Description of Analysis Populations

Univariate one-way repeated measures analysis of variance (ANOVA) test will be used fro statistical analysis of data for primary research question/objective. In addition to 20% inflation of minimum sample size at baseline data collection due to likelihood of poor echo imaging, the number of expected participants decreases over the subsequent 3 data collection points to account for expected mortality in this cohort. All withdrawal will be logged in a case report form. Furthermore the feasibility of 3D imaging is a secondary outcome of this study.

## 14.2 Analysis of Endpoints

Using the assistance of University of Portsmouth statistician, a recommendation of a sample size of 30 in each arm (90 in total), for the test of a single contrast at 0.05 significant level in a one way repeated measures analysis of variance with 3 levels will have 90% power to detect an effect size of 0.15.

In addition to 20% inflation of minimum sample size at baseline data collection due to likelihood of poor echo imaging, the number of expected participants decreases over the subsequent 3 data collection points to account for expected mortality in this cohort. All withdrawal will be logged in a case report form. Furthermore the feasibility of 3D imaging is a secondary outcome of this study.

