## 7.0 STUDY DESIGN

## 7.1 Summary of Study Design

A prospective, cohort study based at a single centre (Queen Alexandra Hospital, Portsmouth). There is no randomization involved in this study. There is no blinding in this study. There will be a single operator for performing the scans due to the level of

Version 1.0 IRAS 247448

professional training and accreditation required to perform a GLS scan. Expected patient participation is 365 days (+/-7) or until mortality whichever occurs first.

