#### 9.0 SAMPLING

The minimum sample size is 108. This was based on the use of repeated measures ANOVA comparing three arms at 4 time points, with the significance level of 5% and power of 90%. This is based on a medium assumed effect size 0.15.

Considering that echo image quality is unknown until after consent and enrolment onto study and 20% inflation to study size was added from the original calculated 89, meaning a total of 108 participants

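### The sample size counts three echo methods as three arms of 30 patients, although every patient has all three, so the stated 90% power is not established

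*Protocol*

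**What the plan says.** Protocol section 14.2 reports "a recommendation of a sample size of 30 in each arm (90 in total), for the test of a single contrast". The model it names is a repeated-measures ANOVA with one factor at three levels, tested at 5%, and it claims that this "will have 90% power to detect an effect size of 0.15".

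Protocol section 9.0 describes the calculation differently: "This was based on the use of repeated measures ANOVA comparing three arms at 4 time points", at 5% significance and 90% power. It adds: "This is based on a medium assumed effect size 0.15". The total comes from this step: "20% inflation to study size was added from the original calculated 89, meaning a total of 108 participants".

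On the design, section 7.1 describes a single-centre prospective cohort and says: "There is no randomization involved in this study". Table 1 in the lay summary and Table 2 in section 10.0 schedule 2D echo, 3D echo and GLS for every patient at each of the four scans. Section 14.1 names a one-way repeated-measures ANOVA for the primary question.

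**The concern.** The three levels of the ANOVA are the three echo methods. They are a within-patient factor, because each patient supplies a value at every level. No patient belongs to a 2D, 3D or GLS arm. In a one-way repeated-measures ANOVA the sample size is the number of patients, so the step from 30 per arm to 90 in total contradicts the model named in the same sentence.

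What is at stake is the meaning of the power statement. A reader takes it that about 90 evaluable patients give 90% power for the primary comparison. That does not follow from the calculation described. The two sections also describe different tests and start from different numbers, so it is unclear which calculation supports 108.

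**Working it through.** **Inputs from the protocol.** Alpha 0.05, power 90%, effect size 0.15, 3 levels, 30 per arm and 90 in total (section 14.2); three arms at 4 time points, starting number 89, 20% inflation, 108 (section 9.0). **Not given:** the scale of 0.15 and the within-patient correlation rho. Both are treated below as assumptions, with a range. Power is from the noncentral F distribution with noncentrality lambda, assuming equal correlation between methods.

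**1. Reproducing the 30.** Take 0.15 as the variance of the level means divided by the error variance, SD²(1 − rho). With n patients each measured at 3 levels, lambda = 3 × n × 0.15, with df 2 and 2(n − 1).
- n = 29: lambda = 13.05, power 0.893.
- n = 30: lambda = 13.5, df 2 and 58, power 0.904.

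So 30 is the smallest number reaching 90%, and it is the total number of patients. This is the 2-df overall test. A 1-df contrast with the same lambda gives 0.951 at n = 30, and 25 patients would be enough.

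**2. Reproducing the 89 and 90.** Take three independent groups with f² = 0.15. Then lambda = 0.15 × N, with df 2 and N − 3.
- N = 87: 0.898
- N = 88: 0.902
- N = 89: 0.906
- N = 90: 0.909

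A total of 88 to 90 is thus the requirement for three separate groups of patients, which this study does not have.

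**3. The actual design on the scale of step 1.** With 90 patients each measured by all three methods, lambda = 3 × 90 × 0.15 = 40.5, df 2 and 178, and power is above 0.999. At 89 it is also above 0.999.

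**4. The actual design with 0.15 as Cohen's f.** Here lambda = 3 × n × 0.15² / (1 − rho), with df 2 and 2(n − 1). For n = 90 the numerator is 3 × 90 × 0.0225 = 6.075.

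| rho | lambda at n = 90 | power at n = 90 |
|---|---|---|
| 0 | 6.08 | 0.58 |
| 0.3 | 8.68 | 0.75 |
| 0.5 | 12.15 | 0.88 |
| 0.53 | 12.93 | 0.901 |
| 0.6 | 15.19 | 0.94 |
| 0.75 | 24.30 | 0.995 |

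**5. The inflation step.** 89 × 1.2 = 106.8, which rounds up to 107. 90 × 1.2 = 108. The planned 108 follows from the 90 in section 14.2, not from the 89 in section 9.0.

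**6. The two sections side by side.** Section 9.0 has three arms at 4 time points. Section 14.2 has a one-way layout with 3 levels and a single contrast. These tests have different degrees of freedom and different noncentrality, so one calculation cannot stand behind both.

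**The case against.** The strongest reply is that 90 patients can give 90% power in this design. If 0.15 is Cohen's f and the within-patient correlation is about 0.53, power is 0.901 at 90 and 0.898 at 89. That is correct, so it would be too strong to say that 90% is impossible here. But the protocol states neither that scale nor any correlation, and on that reading 30 in each arm is still the wrong unit.

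A second reply is that 108 may be perfectly adequate. This also stands. On the scale that reproduces the 30, the number is about three times what is needed. With f = 0.15 and correlation 0.5, all 108 patients would give 0.93.

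A reader might infer the opposite, that the study is badly underpowered, by taking 0.15 as a standardised single contrast. Power would then be 0.29 at 90 patients, and about 468 would be needed. That reading reproduces none of the protocol's figures, so it is a poor guide to what was calculated. It shows only how much hangs on an undefined effect size.

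A reader might also object that two comparisons with 2D EF are planned while power is given for one contrast. How error is controlled across the two is commonly left to a statistical analysis plan, which is not at hand, so no fault is claimed there.

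**Conclusion.** The sample-size statement is wrong as written. Three measurements on the same patient are counted as three arms, in contradiction to the repeated-measures model that the same sentence names. The figure of 30 belongs to 30 patients in total measured three times (power 0.904), and 89 or 90 belongs to three independent groups (0.906 and 0.909). Neither describes 90 patients measured by all three methods. For them, power is above 0.999 on the scale that reproduces the 30, and between 0.58 and 0.995 if 0.15 is Cohen's f and the correlation lies between 0 and 0.75.

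The stated 90% is therefore not established. The direction of the error is not established either, because it depends on the two missing inputs, and the documents do not support calling the study too small. The conflict between sections 9.0 and 14.2 over the test is a further inconsistency. The difference between 89 and 90 is one patient and needs only tidying. These results rest on the noncentral F calculation with equal correlations between methods.

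**What to change.** Keep 108. In sections 9.0 and 14.2:

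- Delete the references to arms and the figure of 30 in each with 90 in total.
- State the number as patients with all three measurements.
- Define the scale of 0.15 and give the assumed within-patient correlation, with its basis.
- Use one design and one starting number in both sections. If 108 is kept with 20% inflation, that number is 90.
- Restate the power for the paired comparisons of 3D EF and of GLS with 2D EF, under the repeated-measures analysis already named in section 14.1. The number of readable patients would be about 86 (108 × 0.8 = 86.4) to 90 (108 / 1.2). As an example of the form, the overall 3-level test with f = 0.15 and correlation 0.5 has power 0.87 at 86 and 0.88 at 90. The inputs are the sponsor's to choose and justify.

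The cost is rewriting two short paragraphs and one repeat of the calculation with the statistician. No extra patients are needed and the primary analysis does not change. The restated power may come out somewhat below 90%, depending on the inputs chosen.

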## 14.3 Procedure for Dealing with Missing, Unused and Spurious Data

Data will be checked for queries every 3 months by the principle investigator and the database updated where possible. These changes will be tracked using an excel document.

## 14.4 Procedures for Reporting any Deviation(s) from the Original Statistical Analysis Plan

Deviations from the original protocol will be documented, with justification and reason.

### 14.5 Interim analysis and criteria for early study termination

Not planned or required

### **15.0 ETHICS**

### 15.1 Participant Confidentiality

The study staff will ensure that the participants' anonymity is maintained. The participants will be identified only by initials and a participants ID number on any electronic and paper database. All documents will be stored securely and only accessible by study staff and authorised personnel. The study will comply with the Data Protection Act 2018 which requires data to be anonymised as soon as it is practical to do so.

## **15.2** Other Ethical Considerations

The study will not be initiated before the protocol and all study relevant material such as the informed consent forms and participant information sheets have received favorable opinion from the Research Ethics Committee (REC), and the respective National Health Service (NHS) Research & Development (R&D) departments. Any changes to protocol or relevant study documents will be approved by the Sponsor. Should an amendment be made that requires REC approval, as defined by REC as a substantial amendment, the changes will not be instituted until the amendment has been reviewed and received favorable opinion from the REC and R&D departments. A protocol amendment intended to eliminate an apparent immediate hazard to participants may be implemented immediately providing that the REC are notified as soon as possible and an approval is requested. Minor amendments as defined by REC as a non-substantial amendment, may be implemented immediately; and the REC will be informed.

All participants will be able to consider continual participation in the study, as per Good Clinical Practice (GCP) guidelines.

Patients who are already enrolled in other research trials will be invited and allowed to participate in the study if they so wish. This was discussed with our PPI representatives who felt that these patients should also have the opportunity to participate in the study, and should

not be excluded.

Patient's privacy and dignity will be maintained as per NHS guidelines for the duration of the echo scan. Although the scan requires access to the chest, the patient will be covered with a sheet or gown and the curtains will be drawn at time of patient interaction.

## 15.3 Declaration of Helsinki

The study will be performed in accordance with the spirit and the letter of the declaration of Helsinki, the Good Clinical Practice Guidelines, the protocol and applicable local regulatory requirements and laws.

## 15.4 ICH Guidelines for Good Clinical Practice

All study staff must hold evidence of appropriate GCP training or undergo GCP training prior to undertaking any responsibilities on this trial. All research staff will monitored by the sponsor to ensure adherence to GCP.

## **16.0 PATIENT PUBLIC INVOLVEMENT (PPI)**

## 16.1 Study design

This proposal originated from clinicians. Lay people will not be participating in data collection or analysis, but will be included as part of the ethical review panel, forming of lay summaries, all steering group meetings and reviewing information sheets

## 16.2 Study implementation

Public and patient involvement will be considered before data collection begins. Patient Research Ambassadors have been identified and invited to attend steering group meetings to give advice on all areas. A national group for Sepsis Survivors has been approached and is happy to be involved in a similar process.

#### 16.3 Dissemination

The study will be included on the Portsmouth ICU and Wessex Intensive Care Society websites research pages which are in public domain. Patient Research Ambassadors will be

invited for advice on areas for public dissemination of results. Lay reports are to be written by PRA's and advice on public dissemination.

#### **17 FINANCING AND INSURANCE**

17.1 Research Costs

£28, 065.14

17.2 Service Support Costs

£1,500.27

#### 17.3 Excess Treatment Costs

No excess treatment costs are expected as this is an observational study.

The NHS indemnity scheme shall apply for the management, design and conduct of the study.

#### 17.4 Study Sponsorship

Portsmouth Hospitals NHS Trust shall act as Sponsor. A Trial Management Group (TMG) will convene quarterly to review the progress of the study. This will consist of the key members listed on the delegation log who are involved in the day to day running of the study. The TMG will oversee day to day management of the study and data quality and will advise the Sponsor of any concerns regardless. Within the Trust a Research Governance Group (RGG) convene regularly to review the progress of Sponsored studies. Any concerns raised with the study will be discussed and addressed at this meeting. In addition, an annual report will be submitted to the research ethics committee for review.

This study will be carried out subject to approval by the Portsmouth Hospitals NHS Trust Research and Development department, NHS Research Ethics Committee and the Health Research Authority. It will be carried out in accordance with the Data Protection act, International Conference for Harmonisation of Good Clinical Practice (ICH GCP) guidelines, Research Governance Framework for Health and Social Care and World Association Declaration of Helsinki (1964) and Scotland (2000) amendments.

## 18.0 TIMETABLE AND ORGANISATIONAL CHART

Month 1-3:	Ethics/R+I approvals, study set-up, CRF finalisation, database testing, writing SOPs etc	All investigators and PRA's	
Month 4-5:	First inclusions, study management meeting and data review, protocol amendments (if required)	All investigators and PRA's	
Month 6-18	Recruitment, data input and cleaning	[name] [name] [name] Research nurses	
Month 18/19	Last recruitment	[name] [name] [name] Research nurses	
Month 21/22 (90days +/- 5 after last recruitment)	Last follow-up visit	[name]	
Month 30/31 (1yr post last recruitment)	Last phone call/follow up	[name] [name]	
2023	Final data cleaning and analysis	[name] UoP statistician	
2024	Dissemination	Investigating team	

## **19.0 RESOURCES, EQUIPMENT AND PHYSICAL FACILITIES**

The following have been identified as resources and equipment required for the duration of the study and these are already part of routine stock:

- GE E9 or E95 TTE machine with 3D and GLS capacity.
- Echocardiography consumables such as electrodes and sonic gel.
- McKesson database/server.
- Consumables for blood tests.

The following requirements are additional tests or services for these patients, and while these facilities are available within this trust they will incur costs:

- Laboratory cost for blood test analysis and reporting.
- Outpatient clinic time for day 30 and 90 follow-up.

### **20.0 DISSEMINATION AND OUTCOME**

Results of this trial will be submitted for external publication in a PubMed cited peer-reviewed journal, with a focus on Intensive Care and echocardiography. The manuscript will be prepared by the Chief Investigator in conjunction with the study team; authorship will be determined by mutual agreement. Any secondary publications and presentations prepared by Investigators must be reviewed by the Chief Investigator.

Available for public access public via PHT and Wessex intensive care Unit websites. The study will also be registered on a public database as part of ethical approval.

There is planned poster presentation at national and international conferences as well as public dissemination as advised by PRA's.

## APPENDIX 1 SCHEDULE OF PROCEDURES

	First 24 hours	At 72 hours	30 days	90 days			
General procedures and safety							
Informed consent	Х						
Demographics	х						
Medical and surgical history	х						
Vital signs (BP, HR)	х	Х	Х	Х			
Weight	х		Х	Х			
PEEP	х	Х	Х	Х			
Adverse events potential	х	Х	Х	Х			
Concomitant therapy	х	Х	Х	Х			
ECG	х	Х		Х			
2D ECHO	Х		Х	Х			
Local laboratory							
Chemistry	Х	Х	Х	Х			
Haematology	Х	Х	Х	Х			
Urinalysis	х			Х			
Hs Troponin	х		Х	Х			
BNP/NT-proBNP	Х		Х	Х			
Investigational tool							
3D ECHO	Х	Х	Х	Х			
GLS	х	Х	Х	Х			
CO (3D ECHO)	х	Х					

